4.3. Coding of Therapies and Medical Terms

The World Health Organization Drug Dictionary (WHO-DD) Version_B3_Q1_2021 will be used to code medications reported in the prior medication, , concomitant medication and medications for CIPO (gastrointestinal symptoms) eCRF pages.

| | |
|---|--|
|  | Statistical Analysis Plan |
| | Sponsor: Alfasigma S.p.A. Protocol: VE-CIP2001/2021 |

The Medical Dictionary for Regulatory Activities (MedDRA) English version 24.0 will be used to code medical terms reported in the Medical History, non-drug therapies or surgical and medical procedures and Adverse Events eCRF pages.

At the end of the study, if an updated version of the dictionaries is available, dictionaries will be updated after Sponsor’s approval, if needed.

4.4. Handling of Drop-Outs or Missing Data

4.4.1. Missing or Partial Dates

For incomplete dates, the imputation will be performed according to the following rule:

- If the date is completely missing, no imputation will be performed
- In case of day missing, the day will be replaced with 15
- In case of day and month missing, the day will be replaced with 1, the month with July

The imputation rules will be applied to the date of CIPO diagnosis, start date for prior medications (including the ), start date of medical history condition, start date for concomitant medications (including the medications for CIPO) and adverse events.

[figure not shown]
In case that these rules led to CIPO diagnosis later than the informed consent date, CIPO diagnosis will be imputed as the informed consent date. Similarly, in case that imputations led to start date later than the end date for concomitant medications and adverse events, the 1st day of the month will be imputed instead of the 15th.

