No ischemic colitis, cerebrovascular, or peripheral vascular events were noted in the prior clinical studies with this compound. No clinically significant changes from pre-treatment have been observed in clinical laboratory test results, measurements, or besides an increase in after the first drug intake; however, increases in were observed after dosing on subsequent visits. These changes were detected only on and not on evaluation. In the thorough In summary, based on PK and PD of Velusetrag, the following potential warnings may be anticipated: Subjects receiving velusetrag should be monitored for exaggerated responses to the GI prokinetic activity of velusetrag (GI AEs), especially upon initiation of treatment. The onset and resolution of GI AEs in the Phase 2 CIC study subjects typically occurred within 1 to 2 days of treatment initiation. Investigators should be aware of the potential for increased heart rate (HR). A modest increase in was observed at both 15 mg and 90 mg in the tQTc study on the first 2 days of dosing, but it was not observed after 6 days evaluation in the Phase 2b gastroparesis study suggested an average compared to baseline (Day 1 predose). However, upon increase in analysis, there was no obvious sign of increase in The clinical significance of the transient effects observed on is unclear, but it was on average at all doses, even on Day 1. There is limited experience regarding administration of velusetrag to subjects who are taking another pharmacologic treatment. Co-administration of strong CYP3A inhibitors may result in an increase in exposure to velusetrag and a decrease in exposure to the active metabolite THRX 830449... Co-administration of strong CYP3A inducers may result in a decrease in exposure to velusetrag and an increase in exposure to the active metabolite THRX 830449. Co-administration of strong P-glycoprotein (P-gp) transporter inhibitors may result in an increase in exposure to velusetrag and the active metabolite THRX 83044. Co-administration of strong breast cancer resistance protein (BCRP) transporter inhibitors may result in an increase in exposure to velusetrag and the active metabolite THRX 83044. There are no data from the use of velusetrag in pregnant women. Animal studies do not indicate direct or indirect harmful effects with respect to reproductive toxicity. As a precautionary measure, it is preferable to avoid the use of velusetrag during It is unknown whether velusetrag/metabolites are excreted in human milk. A risk to the suckling child cannot be excluded.

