10.4 SELECTION OF DOSES IN THE STUDY

Velusetrag 15 mg once daily, have been selected for this study based on the following evidence:

• Prokinetic activity demonstrated in healthy subjects and in patients with CIC and results from a Phase 2 study in subjects with CIC which showed a statistically significant increase in the weekly frequency of SBM at 15, 30 and 50 mg velusetrag respectively, compared with placebo and the difference was statistically significant (p < 0.0001) for all three doses of Velusetrag. The average increase from baseline over the 4-week treatment period was 3.6 SBMs/week at 15 g, 3.3 SBMs/week at 30 mg, and 3.5 SBMs/week at 50 mg Velusetrag compared with 1.4 SBMs/week for placebo. The 50 mg dose was least well tolerated, showing a clinically significantly greater number of reports of headache, diarrhea, nausea,

and vomiting. Diarrhea was reported by 11% to 15% of the Velusetrag subjects compared with 1% of placebo subjects. The incidence of headache was similar for the Velusetrag 15 mg and placebo treatment groups (6% each) and higher for the 30-mg and 50-mg treatment groups (10% and 21%, respectively).

• Results from a Phase 2a and Phase 2b study in subject with idiopathic or diabetic gastroparesis suggested that velusetrag improves gastric emptying. The Phase 2b study was a multicenter, randomized, double-blind, placebo-controlled study to evaluate three doses (5, 15, or 30 mg) of Velusetrag compared to placebo administered once daily for 12 weeks. Velusetrag 15 mg demonstrated improvement in gastric emptying delay on scintigraphy without unexpected concerning safety signals in 65% of subjects, compared to no subjects in the placebo group.

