11.2.2 Visit 2 (Randomization Visit- V2)

The following procedures will be performed at the randomization visit:

Pre-Randomization:

- 1. 2.
- 3. 4.
- 5. Review and record any AEs that occurred since the previous visit.
- 6. Review and record any concomitant medications taken since the previous visit (attention will be paid to prohibited treatments).
- 7. Re-instruct the subject on how to complete the electronic diary (e-diary), which encompasses the
- 8. e-diary review for eligibility according to inclusion **criterium n 4**. Questionnaires will be completed at the clinical center before randomization if not already completed by the subject.
- 9. Confirmation of inclusion and exclusion criteria.
- 10. completion by the subject.
- 11. Randomization (if still eligible).
- 12. Blood collection (in fasting condition) sample (30 mins prior to drug administration) for proof for absorption.
- 13. Treatment dispensing (if subject has been randomized).

Dosing:

First investigational product dose will be administered under the supervision of the study personnel in the morning, on an empty stomach, with water. Time of dosing will be registered.

After the investigational product administration, the following procedures will be completed:

Post-dose:

- 14. 15. 16.
- 17. Retrain the subject on how to use the electronic diary (e-diary), instructing to complete:
 - The subject will be instructed to record, starting from Day 1, investigational
- product intake information daily.

 18. Schodulo port visit and remind the subject to not to take the investigational product in the
- 18. Schedule next visit and remind the subject to not to take the investigational product in the morning of the next visit, but to take the bottle to the clinic.

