For efficacy evaluation after the discontinuation of each treatment, the reference for changes computation is defined as the end of treatment visit for each period: Visit 3 (EOT-1) for period 1, Visit 5 (EOT-2) for period 2, Visit 7 (EOT-3) for period 3 and Visit 9 (EOT-4) for period 4.

| | |
|---|--|
|  | Statistical Analysis Plan |
| | Sponsor: Alfasigma S.p.A. Protocol: VE-CIP2001/2021 |

In case of early switch visit or premature interruption of treatment, the reference for changes computation within each period should be adjusted accordingly based on ESV visits.

First/Last Administration of Study Treatment

Considering the overall study, the date of first administration of treatment (i.e., velusetrag or placebo) is the earliest start date of the 4 periods reported in the “Study treatment dispensed” CRF page while the date of last administration of treatment (i.e., velusetrag or placebo) is the date reported in the “End of treatment disposition” CRF page (i.e., maximum of the last administration of the 4 periods).

According to the study design, subjects will not receive the treatment during the wash out periods. For each study period, the date of first administration of treatment is the start date reported in the “Study treatment dispensed” CRF page on the corresponding SOT visit (i.e., Visit 2 (SOT-1) for period 1, Visit 4 (SOT-2) for period 2, Visit 6 (SOT-3) for period 3 and Visit 8 (SOT-4) for period 4) while the date of last administration of treatment is the last treatment intake date reported in the “Study treatment returned” CRF page on the corresponding EOT visit (i.e., Visit 3 (EOT-1) for period 1, Visit 5 (EOT-2) for period 2, Visit 7 (EOT-3) for period 3 and Visit 9 (EOT-4) for period 4). In case of early switch visit or premature interruption of treatment, the first and last intake within each period should be adjusted accordingly.

Study day

The study day describes the day of the event or assessment date relative to the reference start date, which is defined as the date of Randomization.

The study day will be calculated as the difference between the date of each considered efficacy/safety assessment and the reference start date plus 1 day.

If the considered event starts before the Randomization date, the study day will be calculated as the difference between the date of the assessment and the reference start date. Therefore, the study day will be negative.

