6.4.3. Adverse Events

Treatment-emergent adverse events (TEAEs) will be reported by actual treatment. Adverse events starting on or after the first intake of treatment (i.e., first intake in the period 1) are considered TEAEs. 

| | |
|---|--|
|  | Statistical Analysis Plan |
| | Sponsor: Alfasigma S.p.A. Protocol: VE-CIP2001/2021 |

In addition, TEAEs will be summarized by actual treatment, MedDRA System Organ Class and Preferred Terms considering:

- 
- 

Adverse events will be classified as velusetrag emergent if the last treatment taken before the start of the adverse event was velusetrag, or placebo emergent if the last treatment taken before the start of the adverse event was placebo.

In addition, a summary of TEAEs will be provided by treatment sequence. 

[figure not shown]
- 
- 

[figure not shown]

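### Imputed adverse-event start dates have no visible check against first intake, so some Period 1 events can leave the TEAE tables and, separately, some events can be credited to the other treatment (minor)

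*SAP*

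**What the plan says.** SAP 4.4.1 (Missing or Partial Dates) covers adverse-event start dates together with CIPO diagnosis, medical history and medication dates. When only the day is unknown: "In case of day missing, the day will be replaced with 15". If that puts an adverse event's start after its end, "the 1st day of the month will be imputed instead of the 15th". CIPO diagnosis is also bounded by the consent date. For adverse events the end date is the only visible check.

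SAP 6.4.3 (Adverse Events) then uses the start date twice:

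- TEAE status: "Adverse events starting on or after the first intake of treatment (i.e., first intake in the period 1) are considered TEAEs".
- Attribution: "Adverse events will be classified as velusetrag emergent if the last treatment taken before the start of the adverse event was velusetrag", and likewise for placebo.

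No visible text exempts imputed dates from either use. The date needed for a check is already defined in SAP 4.2: "the date of first administration of treatment (i.e., velusetrag or placebo) is the earliest start date of the 4 periods". That section also defines first intake for each period.

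On timing, Protocol section 8 reports: "The onset and resolution of GI AEs in the Phase 2 CIC study subjects typically occurred within 1 to 2 days of treatment initiation".

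**The concern.** A mid-month date is a reasonable neutral choice for a diagnosis or a past condition. It is not neutral when the date is then compared with a cut-off. Here there are four: first intake in Period 1, which decides whether an event is a TEAE, and the starts of Periods 2, 3 and 4, which usually change the treatment credited. The two kinds of cut-off give two distinct errors. An event on study Days 1-2 can drop out of the TEAE tables, but it cannot move back to another treatment because there is none before it. An event soon after the start of Periods 2-4 cannot drop out, but it can move back to the preceding treatment.

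The days just after a period starts are where the rule errs most, and they are also when Protocol section 8 leads one to expect gastrointestinal events. Protocol 10.4 reports of the same constipation study: "Diarrhea was reported by 11% to 15% of the Velusetrag subjects compared with 1% of placebo subjects". If a similar excess occurs here, moving events between treatments would tend to blur it. The end-date fallback, meant as a safeguard, makes short early events worse because it moves them to the 1st of the month.

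**Working it through.** **Three dated examples**

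1. First dose 20 June; an ongoing event begins 21 June and is recorded as 'June'. Imputed start 15 June, before first intake: not a TEAE.
2. First dose 8 June; an event runs 9-10 June, start recorded as 'June'. The 15th is after the end date, so the start becomes 1 June: not a TEAE.
3. First dose 8 June, so Day 43 (start of Period 2) is 8 June + 42 days = 20 July. An ongoing event begins 21 July and is recorded as 'July'. Imputed start 15 July, which is Day 38, in the first wash-out: credited to the Period 1 treatment.

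**Inputs**

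- Period starts on Days 1, 43, 85 and 127 (Protocol schedule of assessments). Each block includes the wash-out or follow-up after it.
- Four sequences, allocated equally (Protocol 10.3). Of their 12 adjacent-period transitions, 10 change treatment.
- Assumed: first dose equally likely on each of 365 calendar days; month and year of onset known, day missing; end date either absent or complete and 0, 1, 3, 7 or 14 days after onset.

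**Error (a): Period 1 onset on Days 1-2, imputed before first intake**

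With no end date this can be counted by hand.

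- Onset on Day 1 is lost when first intake falls on the 16th or later: 365 - 12 x 15 = 185 dates.
- Onset on Day 2 is lost when onset falls on the 17th or later: 365 - 12 x 16 = 173 dates.
- Share lost: (185 + 173) / (2 x 365) = 358 / 730 = 49.0%.

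With an end date on the day of onset, the fallback adds Day 1 onsets on the 2nd to 14th (13 x 12 = 156) and Day 2 onsets on the 3rd to 14th (12 x 12 = 144). Share lost: (358 + 156 + 144) / 730 = 658 / 730 = 90.1%.

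**Error (b): attributed to the other treatment**

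For onset on the first two days of Periods 2-4, the same calendar shares move back one period, and 10 of 12 transitions change treatment: 49.0% x 10/12 = 40.9% with no end date, and 90.1% x 10/12 = 75.1% with a same-day end.

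For onset uniform over Days 1-168, full enumeration (365 x 168 x 4 = 245,280 cases per row) gives the last two columns.

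| End date after onset | Days 1-2: lost | Days 1-2 of Periods 2-4: other treatment | Uniform onset: lost | Uniform onset: other treatment |
|---|---|---|---|---|
| none | 49.0% | 40.9% | 2.5% | 11.3% |
| 0 days | 90.1% | 75.1% | 4.3% | 10.7% |
| 1 day | 86.8% | 72.4% | 4.0% | 10.1% |
| 3 days | 80.3% | 66.9% | 3.6% | 9.2% |
| 7 days | 67.1% | 55.9% | 2.9% | 8.6% |
| 14 days | 49.0% | 40.9% | 2.5% | 11.3% |

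**Share of all events**

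The documents give no rate of missing days. If 1-5% of events lack the day (an assumption) and onset is uniform:

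- lost from the TEAE tables: 1% x 2.5% = 0.02% up to 5% x 4.3% = 0.2% of events;
- credited to the other treatment: 1% x 8.6% = 0.09% up to 5% x 11.3% = 0.6% of events.

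Early switches and dates lacking the month as well (imputed as 1 July) were not modelled.

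**The case against.** **The rule may exist out of sight.** Text is blacked out directly after the TEAE definition in SAP 6.4.3, and there is a gap inside SAP 4.4.1 between the scope of the imputation rules and the date checks. That imputed dates feed the TEAE rule is the natural reading, but it is not stated. This stands, and makes the point conditional. What is visible is nevertheless a complete rule, and followed as written it misclassifies events.

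**Partial dates should be rare.** Each period starts at a site visit with supervised, timed dosing, and adverse events are reviewed at each visit. Protocol 17.8 requires all requested eCRF items to be entered and 17.10 requires data checks. Events arising off treatment are still described separately under Protocol 15.1.1. This also stands, and is why the point is minor.

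**The highest percentages need an odd record.** A complete end date with an unknown start day is unusual for an event lasting a day or two. The no-end-date row is the more plausible one: 49% for error (a), 41% for error (b).

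**A stronger reading is tempting.** A reader might infer that misattribution around period starts could cancel or even turn round the velusetrag-placebo difference. The documents do not support that. It would need placebo events to bunch on the first two days of each period just as velusetrag events do, and Protocol section 8 gives no placebo timing. It would also need the odd records just described. And it would be a statement about event counts, whereas Protocol 16.3.4 plans numbers and percentages of subjects with at least one TEAE.

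**Conclusion.** The point holds as a minor one, on condition that no hidden text already supplies a rule. As visibly written, SAP 4.4.1 and 6.4.3 together can (a) date Period 1 events before first intake and (b) credit events in Periods 1-4, wash-outs included, to the other treatment. For day-missing events, (a) affects 49% of those with onset on Days 1-2 and no end date, and more when a complete end date lies within about a week of onset. For (b) the share is about 9-11% with uniform onset, and higher just after Periods 2-4 begin.

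These are conditional rates and rest on the calendar assumptions listed. The overall effect depends on a rate of partial dates that the documents do not give; with an assumed 1-5% and uniform onset it stays below 1% of events. With 16 planned subjects, a single moved event could still show in a table, which is reason enough for a short clarification. Nothing here establishes how far subject-level incidence would change.

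**What to change.** First, the sponsor should confirm whether the text not shown in SAP 4.4.1 or 6.4.3 already links imputed dates to first intake. If it does, no change is needed. If not, add to SAP 4.4.1, for adverse events only:

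1. If the known part of the start date and the end date allow onset on or after first Period 1 intake, classify the event as a TEAE. The imputed start may not precede first intake or follow the end date. The exception is an event already captured at the Visit 2 pre-dose step, where Protocol 11.2.2 requires staff to "Review and record any AEs that occurred since the previous visit".
2. If the possible onset interval spans a change of treatment, flag the event in the listing and give a sensitivity summary that assigns it to velusetrag, labelled as a conservative bound.

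Item 1 brings error (a) to 0% in every row of the table but leaves error (b) unchanged, so item 2 is needed as well. Narrowing the interval to the days since the previous visit should not be adopted unless the eCRF records whether an event at a start-of-treatment visit was reported before or after dosing. Otherwise a post-dose event recorded at that visit would be placed under the preceding treatment. The mid-month rule can stay for CIPO diagnosis and medical history.

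**Cost.** A short SAP addition, one derivation change, a listing flag and one summary. With uniform onset the flag would fall on 22-44% of post-dose events lacking the day. Some true screening-week events with a missing day and not identified at Visit 2 would count as TEAEs: with no end date the share rises from 36% to 87%, with an end one day after onset from 0.5% to 14%, and with a same-day end it stays at 0%. Screening lasts at most 7 days, so few events are exposed.

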4.4.2. Handling of Missing Data/Imputation/Censoring Rules

The following rules to impute missing data will be applied for the efficacy primary endpoint and further details are provided in section 6.3.1.

Missing pairs (treatment difference velusetrag minus placebo) can occur when at least one of the following is missing:

- Pre-treatment velusetrag value missing
- End of treatment velusetrag value missing
- Pre-treatment placebo value missing
- End of treatment placebo value missing

| | |
|---|--|
|  | Statistical Analysis Plan |
| | Sponsor: Alfasigma S.p.A. Protocol: VE-CIP2001/2021 |

These rules of imputation will be applied only if a subject starts the period of interest (i.e., if he/she performs the corresponding start of treatment visit).

The above approach will be used for the FAS and as sensitivity analysis for mFAS1, , PPS.

No missing imputation will be applied for secondary efficacy endpoints.

4.4.3. Handling of Drop-Out Subjects

Subjects who discontinue the study for any reason will be analyzed for efficacy and safety purposes.

4.5. Multiple Comparison/Multiplicity

[figure not shown]
Not applicable.

[figure not shown]
4.6. Multicentre Studies/Center Pooling

The data from all sites will be pooled and analyzed. Given the small sample size, no analysis will be performed by site or country.

5. ANALYSIS POPULATIONS

The following analysis populations are defined based on the study protocol:

- **Screened population:** all subjects who provided informed consent. A screening failure is defined as a screened subject who has not been randomized to treatment.
- **Randomized population:** all screened subject who has been randomized to treatment.
- **Safety Set (SS):** all treated subjects (i.e., subject who received at least one  of the investigational product or placebo).
- **Full Analysis Set (FAS):** all randomized and treated subjects.
- **Modified Full Analysis Set 1 (mFAS1):** all subjects responder/naïve to   randomized and treated who reported data on the primary endpoint at least once during a velusetrag treatment period and at least once during a placebo treatment period in the same cycle.

- 

| | |
|---|---|
|  | Statistical Analysis Plan |
| | Sponsor: Alfasiigma S.p.A. Protocol: VE-CIP2001/2021 |

- **Per Protocol Set (PPS):** all subjects in the mFAS1 who fulfil the study protocol requirements in terms of compliance to treatment and collection of primary efficacy data, and with no major deviations that may affect study results.

For the PPS analysis, if within a period, the compliance is below 80%, the primary endpoint data of this period will be excluded from the analysis. E.g., if compliance data are 100%, 100%, 60%, 60%, the subject is included in the PPS (overall compliance at 80%) but the observations of the third and fourth period are excluded.

The complete list of deviations will be defined in a specific protocol deviation handling plan and a blind data review meeting will occur prior to unblinding. The decisions for exclusion of subjects from the PPS will be taken in a blinded manner and documented.

Analysis on the SS will be performed according to the actual treatment received.

Analysis on the FAS, mFAS1,  will be performed according to the treatment and stratum assigned at randomization following the intent-to-treat principle.

[figure not shown]
Analysis on the PPS will be performed according to the actual stratum, while no cases of study treatment different from the randomized one can belong to the PPS (i.e., subjects receiving a study treatment different from the randomized one will be excluded from the PPS).

